#### 4. Eligibility Criteria

Identify the criteria for inclusion and exclusion.

Those who satisfy inclusion/exclusion criteria and screening procedures will be enrolled in this pilot study. Subject enrollment will include all ethnic groups and both sexes. Every effort will be made to enroll appropriate gender and minority/ethnic background representation that reflects the general population distribution seen at the University of California, Irvine, Dermatology Department Clinics.

##### Inclusion Criteria

Subjects must meet the following criteria:

- Ability to understand and carry out subject instructions or be represented by a legally authorized guardian or representative
- All ages. Patients younger than 4 may have difficulty cooperating with the OCT measurements because each measurement requires the patient to remain still for approximately 30 seconds.
- Seeks and is scheduled for laser treatment of a skin lesion

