### 3. Research Procedures

Provide a detailed chronological description of all research procedures.

A screening log of all potential subjects will be kept at our site. All screening evaluations must be reviewed by the investigator to establish patient eligibility prior to registering the patient for this study.

The following screening evaluation should be completed for all subjects on the first visit:

- Informed consent and photograph release form
- Focused medical history including diagnosis of lesion if applicable. This includes general questioning about the patient's health, well-being, allergies, and medications, and history of the skin lesion in question as identified by the patient and confirmed by the physician.
- Focused skin exam. This includes a detailed medical examination of the skin lesion in question.
- Documentation of area of skin to be studied. This will be determined by the patient's indication and confirmed by the physician.

On visit number one of the study, patients will consent to the study, and an area of skin to be studied will be photographed by digital photography. If the study area is on the face, subjects will be offered to protect their identity.

Non-invasive imaging will then be performed with OCT. Each individual scan with OCT takes about 30 seconds to complete, and we may perform multiple scans on larger lesions. Based on the data and information obtained, the appropriate laser device and settings will be applied for the most optimal treatment to achieve the best results with the fewest side effects. Then laser treatment will be performed on the lesion of interest. Immediate post-treatment imaging and photography will be conducted to assess the results of the treatment. This first visit should take no more than 1.5 hours: approximately 20 minutes for a medical history and focused skin examination, 30 minutes for imaging including photographs, and 30 minutes for laser treatment. These times are all maximums and will likely be shorter. The patient may take as long as needed to consent and is permitted to take the consent form home and return another day to sign and enroll.

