Some subjects may be asked to participate in more than one imaging session. They will have the option of refusing participation in additional sessions. Follow-up examinations will be performed every 4 weeks. During these examinations, photography and imaging of the lesion of interest will be performed with optional laser treatments to be performed at the discretion of the treating physician and the patient. If no laser treatment is necessary, then the visit should take no more than 30 minutes for a quick follow-up and imaging. Additional laser treatment will require no more than 30 minutes to complete. The number of follow-ups is also determined at the discretion of the treating physician and the patient but could range from 1 to 6 depending on the response of the lesion to treatment.

Matched prospective controls will be gathered to be compared against the imaged, treated, experimental group. The prospective controls will be matched to age, gender, skin type, and type of skin lesion. They will be gathered via a retrospective chart review by abstracting and data directly from our own records.

Describe the duration of a subject's participation in the study. If there are sub-studies, include duration of participation in each sub-study.

For each visit: history and skin examination-30 minutes, imaging – up to 30 mins, and laser treatment – up to 30 mins. These are all maximums and will likely be shorter.

At a follow-up, the patient may or may not receive a laser treatment thus shortening the visit. A patient would be expected to have 1-6 follow ups depending on their response to treatment, so their maximum time in this study could range from about 1 to 6 months. Each follow-up visit is made about 4 weeks from the prior visit.

List data collection instruments (e.g., measures, questionnaires, interview questions, observational tool, etc.).

*Investigator-authored, non-standardized, or un-validated measures must be submitted for review.*

Standardized photography,  
OCT

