The two studies of laser treatment with OCT imaging assistance, Weibel et al. 2016 and Weibel et al. 2018, demonstrated that the depth of lesions and the size and density of the surrounding blood vessels varied widely across patients with burn and traumatic scars and vascular hemangiomas, and that some lesions appearing to be superficial had a much deeper component than could be visualized or palpated. Based on this insight, we hypothesized that laser treatment with imaging assistance would enable dermatologists to calibrate the laser parameters precisely to the actual depth of a lesion and the actual size and density of the surrounding blood vessels; as a result, at least 60% ( $\pm 20\%$ ) of the lesion of any type would be cleared after one laser treatment with imaging assistance as compared to 40% ( $\pm 20\%$ ) without imaging assistance.

A sample size of 34 patients, including 17 patients prospectively treated with laser and imaging assistance for lesions of any type and 17 prospective controls who received laser treatment without imaging assistance, would yield 80% power to test the aforementioned hypothesis using a two-sided two-sample t test at 5% significance level.

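### Lesions already treated with laser can enter either group, and neither the matching nor the primary test accounts for it, so past treatment can mimic or mask an OCT effect

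*Combined protocol and SAP*

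**What the plan says.** **Eligibility (Section 3).** The treatment-related inclusion criterion is "Seeks and is scheduled for laser treatment of a skin lesion". The single exclusion concerns the ability to follow instructions. Earlier laser treatment of the lesion is not mentioned.

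**Comparability of the groups (Section 6).** Research Procedures states: "The prospective controls will be matched to age, gender, skin type, and type of skin lesion". The controls are called prospective but are collected by retrospective chart review, and the Statistical Analysis Plan describes them as previous, conventionally treated patients. Study Design adds stratification by lesion type and size, and asks that controls have comparable treatment and length of follow-up.

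**Data collected.** The first-visit evaluation includes "history of the skin lesion in question as identified by the patient and confirmed by the physician", but this history has no stated role in eligibility, matching or analysis. The screening lists in Section 3 do not name earlier treatment for either group.

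**Analysis and sample size (Section 6, Statistical Considerations).** The primary comparison is an unadjusted two-sample t-test at each treatment. The planning hypothesis is stated as the share of the lesion that "would be cleared after one laser treatment with imaging assistance as compared to 40" percent without imaging. The 34 patients "would yield 80% power to test the aforementioned hypothesis using a two-sided two-sample t test at 5% significance level".

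**The concern.** The groups are not randomised and arise by different routes. OCT patients may be the team's own patients, members of patient foundations or people on a website registry; controls come from past clinic records. If the share of previously treated lesions differs between the groups, and such lesions respond differently or are graded from a different starting point, the t-test attributes that difference to OCT. The test is repeated at each treatment and the numbering of treatments carries forward, so the problem is not confined to the first time point. Blinded grading of photographs does not help, because the difference lies in the lesions and not in the graders. If earlier treatment is not abstracted for the controls, it cannot be adjusted for at analysis.

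**Working it through.** **Step 1: is earlier treatment controlled anywhere?**

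| Place | What it uses | Earlier laser treatment? |
|---|---|---|
| Inclusion and exclusion criteria | planned laser treatment; ability to follow instructions | not mentioned |
| Screening lists, Section 3 | age, lesion type and location in both groups; willingness and ability to take part (OCT); clearance and response (controls) | not named |
| Study Design | lesion type and size; comparable treatment and follow-up | not named |
| Research Procedures, matching | the four listed factors | not listed |
| Research Procedures, first visit | lesion history taken | given no role |
| Statistical Analysis Plan | two-sample t-test, no covariates | not adjusted for |

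**Step 2: is the starting point fixed?** For OCT patients, largely yes: Research Procedures has the study area photographed at the first visit, before the laser treatment. For controls, no text says which charted treatment is treatment one or which photograph is the comparator.

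**Step 3: reproduce the planned sample size.** Inputs from Sample Size Determination: means 60 and 40, SD 20 (the plus/minus figure read as an SD), 17 per group, two-sided 5%.

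- Standard error of the difference = 20 × √(2/17) = 6.86 points.
- Noncentrality = 20 / 6.86 = 2.92 on 32 degrees of freedom.
- Exact power is 80.7% with 17 per group and 78.1% with 16. The stated 17 per group reproduces.

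**Step 4: effect of a bias b.** Write b = (difference between groups in the share of previously treated lesions) × (difference in mean clearance between treated and untreated lesions). The documents give neither term, so the values below are assumptions. For example, 0.2 × 10 = 2, 0.5 × 10 = 5 and 0.5 × 20 = 10 points. With no OCT effect the noncentrality is b / 6.86. With a true 20-point effect and the bias against OCT it is (20 − b) / 6.86.

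| b (points) | Noncentrality, no effect | False-positive risk | Noncentrality, true effect 20 | Power |
|---|---|---|---|---|
| 0 | 0 | 5.0% | 2.92 | 80.7% |
| 2 | 0.29 | 5.9% | 2.62 | 72.1% |
| 5 | 0.73 | 10.9% | 2.19 | 56.4% |
| 10 | 1.46 | 29.3% | 1.46 | 29.3% |

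These figures hold the SD at 20. Mixing treated and untreated lesions also widens the SD, to 20.6, 20.5 and 21.8 in the three examples if the shares are centred on one half. The false-positive risks then become 5.9%, 10.6% and 25.4%, and the powers 69.6%, 54.5% and 25.4%. The picture does not change.

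**Step 5: could an imbalance arise by chance?** If half of all lesions had been treated before (assumed), two groups of 17 would differ in that share by 20 percentage points or more with probability 0.23, even without any systematic difference in recruitment.

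**The case against.** **No imbalance is shown.** Controls come from the same clinic and could equally be part-way through a course. That stands: the documents show that earlier treatment is uncontrolled, not that the groups will differ or in which direction. A reader might infer from the foundation and own-patient recruitment that OCT lesions will be the more heavily treated; nothing in the text establishes this.

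**The plan already asks for comparable treatment and follow-up, and stratifies by lesion size.** This bears on comparability, and size may partly reflect past treatment. But the wording does not name earlier treatment and does not fix the index treatment for controls.

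**The plan's clearance figures might seem to give the size.** A reader might take 40% after one treatment and 65% after three, and infer that later treatments clear only 1 − √(35/60) = 23.6% of the remainder each, 16.4 points less than the first. The documents do not support this. The 65% is the plain mean of four outside results, (50 + 70 + 50 + 90) / 4, and the 90 is itself a one-treatment result. The 40% is a separate estimate after an unquantified adjustment for the local population. The two figures are not points on one response curve. A constant rate fits either figure alone: 1 − 0.35^(1/3) = 29.5% per treatment gives 65% after three, and 40% per treatment gives 1 − 0.6³ = 78.4%. Neither implies a first-treatment advantage.

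**Grading against the original lesion might seem to credit 40 extra points for one earlier treatment.** Even on the rates just rejected, total clearance would be 1 − 0.60 × 0.764 = 54% against 40%, about 14 points. For OCT patients the first-visit photograph makes such grading unlikely in any case.

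**This is a pilot.** True, but the plan claims 80% power for a two-sided test between the groups, so the comparison should be protected.

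**Conclusion.** The gap is real and the fix is a cheap improvement. Eligibility admits previously treated lesions, no design or analysis step accounts for them, and the index treatment and baseline photograph are undefined for the chart-review controls. The resulting bias can favour or disfavour OCT, and its size and direction cannot be derived from the documents. The range in the working rests on assumed biases of 2 to 10 points, 17 per group and the plus/minus 20 read as an SD. It shows that a bias well below the 20-point planned effect would matter. The planned sample size is not in question.

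**What to change.** 1. **Baseline.** In both groups, define the index (study) treatment, take the photograph made immediately before it as baseline, and count treatments from there.
2. **Data.** Record earlier laser treatment of the study lesion (none v any, and the number), from the first-visit history for OCT patients and from the chart for controls. Add it to the control data list in Section 3.
3. **Comparison.** Add none v any to the matching factors in Research Procedures. Where no such match is available, adjust the primary comparison for it. None v any is coarse, which is why the number should be recorded as well.

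**Cost.** A few lines of protocol wording and one or two abstraction fields, drawn from a history already taken and charts already reviewed. The downside is a somewhat smaller pool of eligible controls, by an amount the documents do not allow one to estimate. On the stated inputs, 17 per group is unchanged.

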##### Exclusion Criteria

Any of the following will exclude participation in the study:

- Inability to understand and/or carry out instructions

If eligibility is based on age, gender, pregnancy/childbearing potential, social/ethnic group, or language spoken (e.g., English Speakers only), provide a scientific rationale.

Not applicable: Subject eligibility is not based on these factors.

#### SECTION 4: RECRUITMENT METHODS

Check any of the following methods that will be used to recruit subjects for this study:

This study involves no direct contact with subjects (i.e., use of existing records, charts, specimens).

Specify database or IRB-approved protocol number (HS#), if applicable: <Type here>

Advertisements, flyers, brochures, email, Facebook, and/or other media.

Specify where recruitment materials will be posted: Recruitment emails may be sent out to the UC Irvine Campus through approved channels such as the SOM Dean's Office. We will also contact foundations with interest in this topic including The Sturge Weber Foundation and National Rosacea Society and will have then send email advertisements to their members and newsletter subscribers.

If subjects will be recruited by mail, e-mail, or phone, specify how their contact information will be obtained: Any subject recruited by email would be contacted through a general email list from those described above.

*Submit recruitment materials for IRB approval.*

The study will be listed on Clinicaltrials.gov. *All clinical research must be registered.*

The study will be listed on the UC Irvine Health Clinical Trials web page.

*Submit the UCIMC Standard Research Recruitment Advertisement for IRB approval.*

The UCI Social Sciences Human Subjects Lab/Sona Systems will be used.

*Submit the Social Science Human Subject Pool Recruitment Advertisement for IRB approval.*

Referral from colleagues

1. Study team will provide colleagues with UCI IRB-approved recruitment materials for distribution to potential subjects (e.g., recruitment flyer, introductory letter);
1. An IRB-approved recruitment letter will be sent by the treating physician. The letter will be signed by the treating physician and sent to his/her patients to inform them about how to contact study team members; and/or
2. Colleagues obtain permission from interested patient to release contact information to researchers.
3. Study team does not have access to patient names and addresses for mailing.
4. If colleagues will screen their patients' medical records to determine subject eligibility and approach patients directly about study participation: *Complete Appendix T to request a partial waiver of HIPAA Authorization.*

*Submit recruitment materials for IRB approval.*

Study team will contact potential subjects who *have given prior permission to be contacted* for research studies.

Specify when and how these individuals granted permission for future contact: Study team members will also contact potential subjects by phone that have provided permission to be contacted for participation in future research studies

Many subjects contact the Beckman Laser Institute or other UC Irvine clinics who are interested in studies. There is no specific data base.

Study team members will approach their own patients, students, employees for participation in the study.

Study team will screen UCIMC medical records to which they have access to determine subject eligibility. The patients' physicians will approach patients directly about study participation.

*Complete Appendix T to request a partial waiver of HIPAA Authorization.*

Other Recruitment Methods: Study team members will also contact potential subjects by phone that have provided permission to be contacted for participation in future research studies. These patients have contacted us through our website registry, [www.uciderm.com](http://www.uciderm.com), and have consented online for us to contact them for future studies. Study team members will approach their own patients, students, employees for participation in the study. Potential subjects that are contacted by phone will be attempted to be reached a maximum of 3 times over the period of 3 months.

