### **SECTION 3: SUBJECT POPULATION(S) (INDIVIDUALS/RECORDS/SPECIMENS)**

#### **1. Subjects To Be Enrolled on this UCI protocol (Persons/Records/Biospecimens)**

1. Complete the table of subject enrollments below. *Include additional rows for subject category/group, as needed.*
2. If the study involves the use of existing records or biological specimens, specify the maximum number to be reviewed/collected and the number needed to address the research question.

Category/Group (e.g., adults, controls, parents, children)	Age Range (e.g., 7-12, 13-17, adults)	Maximum Number to be Consented or Reviewed/Collected (include withdrawals and screen failures)	Number Expected to Complete the Study or Needed to Address the Research Question
Study Group	All ages	30	17
Control group (prospective controls)	All ages	30	17
Total: 60			

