### **2. Study Design**

Include an explanation of the study design (e.g., randomized placebo-controlled, cross-over, cross-sectional, longitudinal, etc.) and, if appropriate, describe stratification/ randomization/blinding scheme.

This is a longitudinal study with matched prospective controls. The patients will undergo treatment and follow-up over the course of 1-7 months. Their results will be compared to that of matched prospective controls with similar treatment and follow duration. There is no placebo, and patients will not be blinded.

Patients will be stratified based on their lesion type and the size of the lesion as these factors may impact the response to laser treatment and thus the data measurements from OCT. Photographs of the patients' treated lesions will be rated for lesion improvement by blinded physicians. OCT measurements of the lesion of interest will be used to validate the improvement and cosmetic results.

Provide precise definitions of the study endpoints and criteria for evaluation; if the primary outcomes are derived from several measurements (i.e., composite variables) or if endpoints are based composite variables, then describe precisely how the composite variables are derived.

Primary endpoints include photographic improvement of the lesion(s) of interest after 1 or more laser treatments. Two board certified dermatologists grade the degree of improvement (clearance of the lesion) in quartiles (no clearance=0-25, mild clearance=26-50, good clearance=51-75, excellent clearance=76-95, complete clearance=96-100). It will be up to the experienced treating dermatologist to determine the number of treatments necessary for maximum clearance of the lesion(s).

Secondary endpoints include measurements with OCT, which show reduced lesion thickness, lesion size, size of blood vessels, and density of blood vessels, and number of superficial blood vessels.

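### No rule says which scheduled laser patients are approached for OCT-guided treatment, so selection by physicians and by volunteers can be confounded with the OCT effect

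*Combined protocol and SAP*

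**What the plan says.** **Who is approached.** Section 4 states that "Study team members will approach their own patients, students, employees for participation in the study". The same sentence is repeated in the typed answer under Other Recruitment Methods. The record-screening item says that the treating "physicians will approach patients directly about study participation".

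**Other routes.** Section 4 also says "Recruitment emails may be sent out to the UC Irvine Campus through approved channels such as the SOM Dean's Office", plans mailings through two patient foundations and phone contact with website-registry volunteers, and notes that "Many subjects contact the Beckman Laser Institute or other UC Irvine clinics who are interested in studies". It does not say how many enrolments are expected by each route.

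**Eligibility.** Section 3 (Eligibility Criteria) admits patients of any age who are scheduled for laser treatment of a skin lesion and can follow instructions or are represented by someone authorised to act for them.

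**Design and controls.** Section 6 (Study Design) says: "This is a longitudinal study with matched prospective controls". No allocation scheme follows. Patients are stratified by lesion type and size, and blinded physicians rate the photographs. Section 6 (Research Procedures) matches controls on age, gender, skin type and lesion type, and takes them from the team's own charts by retrospective review.

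**Log and analysis.** Research Procedures says: "A screening log of all potential subjects will be kept at our site". The Statistical Analysis Plan compares the groups with a two-sample t-test at each treatment and mentions neither the matching nor the strata.

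**The concern.** A physician deciding whether to raise the study with a patient has already seen the lesion and knows its treatment history. If patients expected to respond well are approached more often, or difficult cases are, the OCT group starts with a different prognosis from the controls, even within the same age, gender, skin type and lesion type. People who answer a mailing or join a registry may differ too, for example in motivation or in how many treatments they have already had.

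The eligibility criteria hardly narrow the field, so they do not limit this discretion. The t-test attributes any resulting difference in clearance to OCT guidance, in either direction. A reader of the final report could not judge the size of the problem, because the plan does not call for a record of eligible patients who were never approached.

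**Working it through.** **Inputs** (Sample Size Determination): mean clearance 60% with OCT and 40% without, a difference of 20 points; ±20% in each group, read as the SD; 17 per group; two-sided t-test at 5%; 80% power.

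**1. The plan's own figure.** The normal approximation, n = 2(1.96 + 0.84)² × 20²/20² = 15.7, gives 16 per group. The exact test uses the noncentral t distribution with

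- df = 2n − 2 = 32, critical value 2.037
- standard error = 20 × √(2/17) = 6.86
- noncentrality = 20/6.86 = 2.92

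Power is 80.7% at 17 per group and 78.1% at 16. The stated 34 patients are therefore the exact t-test answer, and nothing here disputes them.

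**2. No OCT effect, groups differ in prognosis by b points.** The noncentrality becomes b/6.86 at 17 per group. At 30 per group, the enrolment cap, the standard error is 20 × √(2/30) = 5.16. The values of b are assumptions.

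| b (points) | Noncentrality, n = 17 | Rejection, n = 17 | Rejection, n = 30 |
|---|---|---|---|
| 2.5 | 0.36 | 6.4% | 7.6% |
| 5 | 0.73 | 10.9% | 15.9% |
| 7.5 | 1.09 | 18.6% | 29.8% |
| 10 | 1.46 | 29.3% | 47.8% |

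Enrolling more patients makes this worse, because a fixed bias is then tested with more precision.

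**3. Selection in the other direction.** If the true gain is 20 points but harder lesions are approached, the net difference is 20 − b. With b = 5 (net 15) power falls from 80.7% to 56.4%. With b = 10 (net 10) it falls to 29.3%.

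**4. How much selection would produce such gaps?** Suppose the physician's impression correlates ρ with later clearance, and only the most favourable fraction f is approached, while controls are unselected. The gap is ρ × 20 × φ(q)/f, where φ is the standard normal density and q its upper-f point.

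| ρ | f | Gap (points) | Rejection, n = 17 |
|---|---|---|---|
| 0.3 | 0.75 | 2.5 | 6.5% |
| 0.5 | 0.75 | 4.2 | 9.2% |
| 0.3 | 0.50 | 4.8 | 10.4% |
| 0.5 | 0.50 | 8.0 | 20.4% |

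Both ρ and f are assumptions. Under this model, moderate steering gives gaps of roughly 2.5 to 8 points; a 10-point gap needs stronger selection than any row here.

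**5. What the safeguards cover.** Matching and stratification together address age, gender, skin type, lesion type and lesion size. Severity, prior treatment and expected response are left out. Blinded rating protects the reading of the photographs, not the make-up of the groups.

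**The case against.** **Physicians are not the only gatekeepers.** This stands. A reader might infer that physician choice alone determines the OCT group. Section 4 lists several other routes, and each patient must also consent. Those routes add volunteer selection, however, and do not remove selection by physicians.

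**No stated belief about which lesions benefit.** This also stands. A reader might take the sample size text to show that physicians expect certain lesions to gain. It predicts better clearance for any lesion type, and its remark that "some lesions appearing to be superficial had a much deeper component than could be visualized or palpated" concerns a feature that cannot be seen when the patient is approached. The point needs only that physicians can see severity and know the treatment history.

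**Safeguards exist.** Matching, stratification by type and size, and blinded rating do reduce bias. They do not close the gap, and the planned test uses neither the matching nor the strata.

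**The log already covers all potential subjects.** It is a sound base, but nothing defines that group as every scheduled eligible patient, asks why someone was not approached, or commits to reporting the flow.

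**The error rates are generic.** True: they would fit any bias in a study of this size. They show sensitivity, not likelihood.

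**It is a pilot with an openly non-randomised design.** Fair as a reason not to demand randomisation. But the plan makes a powered comparison at the 5% level, so the make-up of the groups matters.

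**Conclusion.** The point holds in a limited form. Entry to the OCT group depends partly on whom the study physicians choose to approach and partly on self-referral. No rule governs the first and no record is required of those not approached, and the unadjusted primary test cannot separate selection from the OCT effect. At 17 per group and SD 20, an assumed gap of 5 or 10 points raises type I error from 5% to 10.9% or 29.3%. The documents show that such bias is possible; they do not show that it is present or how large it is.

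Three further inferences are not supported:

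- **That patients not approached become controls.** Section 3 keeps out the data of those who decline and is silent on those never approached. The Statistical Analysis Plan describes controls as previous patients, who may have been treated before enrolment began.
- **That 30 controls will be consented and could simply be randomised.** The enrolment table has a row beginning "Control group (prospective controls", but its maximum counts people consented or records reviewed, and Research Procedures describes chart review.
- **That the protocol declares the treating team unblinded.** Study Design says this only of patients. The team must know the group, since it sets the laser from the OCT data, but that is a deduction.

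**What to change.** 1. **Section 4:** state that every patient scheduled for laser treatment who meets the Section 3 criteria is approached, in order of appointment, until the target is reached. Enrolees must be scheduled for laser treatment in any case, so the rule can also take in email, foundation and registry volunteers once they have an appointment.
2. **Section 6 (Research Procedures):** have the screening log record the recruitment source of each patient and the reason for each one not approached or who declined.
3. **Reporting:** commit to showing that flow with the results: eligible, approached, consented and treated, by recruitment source.

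The cost is protocol wording and extra columns in a log already kept. The sample size stays at 17 per group with 80.7% power. The real downside is that physicians lose discretion over whom to approach.

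This reduces and documents selection into the OCT group. It leaves volunteer selection visible but not removed, and it does not by itself make chart controls comparable. How controls are chosen, with clearance and response among the items screened, needs its own remedy.

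Random allocation within the lesion-type and lesion-size strata would deal with selection between the groups. It is an option only if the sponsor first reconciles the sections that call the controls prospective (enrolment table, Study Design, Sample Size Determination) with those that describe chart review or previous patients (Research Procedures, Statistical Analysis Plan), and settles on truly prospective controls. If controls now come from charts, that means recruiting, consenting and following 17 more patients, a larger design change outside this fix.
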